5.3 Handling of Missing data

Medications with a missing start date and whose stop date is either unknown or after the date of the first dose of study drug, will be considered concomitant. Medications with a missing start date and whose stop date is prior to the date of the first dose of study drug, will be considered as prior medications.

Where the adverse events start dates of year part are missing then the value will not be imputed. For the partial missing situation (month or day missing), the value will be imputed for the analysis purpose.

Missing pattern	Start Date / Pre-Dosing	End Date / Post-Dosing
completely missing	leave missing	
missing year	leave missing	
missing month	set to 'JAN'	set to 'DEC'
missing day	set to '01'	set to last day of the month
missing month and day	set to '01JAN'	set to '31DEC'
missing time (concomitant medication)	set to '00:00:00' missing hours: 0 missing minutes: 0 missing seconds: 0	set to '23:59:59' missing hours: 23 missing minutes: 59 missing seconds: 59
missing time (adverse event)		set to '23:59:59' missing hours: 23 missing minutes: 59 missing seconds: 59

These rules apply to AE and concomitant medication. For AE, beginning/end date of AE, first date of study treatment and date of death are considered to avoid inconsistency.

For Visit data other than efficacy, only missing time rules apply. For efficacy visit data, no imputation is made. For birth date, set missing month to '06' and/or set missing day to '15'.

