#### 4.4 CONCOMITANT THERAPY

Data on details of prior and concomitant medications (e.g., prescription drugs and over-the-counter drugs) should be reported to the Investigator and recorded in the Concomitant Medications section of the electronic case report form (eCRF) as follows:

		Prior to and throughout the study	
		More than 4 weeks prior to baseline	Within 4 weeks prior to baseline until the end of study
NMO/ NMOSD treatments	Relapse prevention 	indication, drug name  , dose, frequency, route, first administration (date), last administration (date)/continuing at the end of the study	
	Rescue therapy 	indication, drug name  , route, first administration (date), last administration (date)/continuing at the end of the study	
		-	dose, frequency
	Pain	-	indication, drug name  , route, dose, frequency, first administration (date), last administration (date)/continuing at the end of the study
Other treatments		-	indication, drug name  , route, first administration (date), last administration (date)/continuing at the end of the study

1) For concomitant medication used more than 2 years prior to baseline, the following information is mandatory: indication, drug name, first administration (date) and last administration (date)/continuing at the end of the study. For concomitant medication used less than 2 years prior to baseline, the information listed is mandatory.

2) Trade name is preferred.

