**1. Potential relapse reported by the patient**

If a patient becomes aware of signs or symptoms which might indicate a relapse, the patient will contact the site immediately and return to the site for an extra visit as soon as possible with a target date set for no more than 3 days after reporting the symptoms to the site. The examining assessor must perform the EDSS/FSS assessment within seven days after the patient reports the symptoms to the site. The list of assessments to be obtained at the extra visit at relapse is listed in [Appendix 1](#). The Investigator should treat the patient as necessary based on his/her evaluation of the symptoms after the completion of relapse assessments. MRI findings might be supportive for evaluation of relapse.

[figure not shown]
If a patient has difficulty visiting the study site within three days due to severity of the relapse, the patient can visit a local clinic/hospital for immediate management of a relapse, and then visit the study site as soon as possible (which may be during or immediately after rescue therapy for clinical relapse). Alternatively, the examining assessor may visit the local clinic/hospital to conduct the EDSS/FSS assessment during rescue therapy for a clinical relapse. Even in this case, the examining assessor must perform the EDSS/FSS assessment within seven days after the patient reports the symptoms to the site.

If the patient is seen at a clinical facility other than the study site, the patient should show the patient ID card which includes the investigator's contact

information to the treating physicians/nurses at the local clinic/hospital and the study site must make every effort to obtain medical records from the facility, including information on treatment administered and the nature of the symptoms and signs observed.

The assessment of a relapse is summarized in [Figure 2](#).

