5.10.2 Primary Efficacy Variable

The primary efficacy analyses will be based on the ITT population. Supportive evaluations will be performed using the PPS population.

The primary efficacy endpoint is TFR based on protocol-defined relapses confirmed by the CEC with EDSS/FSS assessment performed by the examining assessor within 7 days after relapse symptoms were reported to site by the subject. TFR is defined as the time from the date of the randomization until the first occurrence of relapse throughout the study. Time point of relapse onset is defined as time at which the subject experiences any new or worsening neurological NMO representing clinical relapse(s) which is later confirmed by the CEC as protocol-defined.

Censor is defined as the earliest day of 1) the end of double blind period for efficacy analysis, 2) switching or increasing the baseline treatment (for details on the identification of the switch and increase in baseline therapy see appendix 7.4), or 3) receiving rescue therapy for clinical relapse.

The primary analysis of the study is to test the equality of the TFR distribution based on protocol-defined relapse in the SA237 + baseline treatment (SA237) and Placebo + baseline treatment (placebo) arms:

$$H_0: TFR_{SA237} = TFR_{\text{placebo}} \text{ versus } H_1: TFR_{SA237} \neq TFR_{\text{placebo}}$$

A stratified two-sided log-rank test using strata of baseline ARR (one vs. more than one) and geographical region (Asia and EU/Other) will be used.

The Kaplan-Meier method will be used to estimate the TFR based on protocol-defined relapses distribution for each treatment group. The Kaplan-Meier curve will provide a visual description of the differences across treatment groups. In addition, estimates of the treatment effect will be expressed as hazard ratio and 95% CIs using a stratified (baseline ARR and geographical region) Cox proportional-hazards model (Exact method will be used for tie data). Treatment by covariate interactions will be assessed by including the pairwise interaction terms in the Cox proportional-hazards model.

The following summary tables, figures and analysis will be provided for the ITT and PPS:

- A summary table of Kaplan-Meier estimate of TFR (protocol-defined relapse) will be presented by treatment group.
- A figure of Kaplan-Meier estimate of TFR (protocol-defined relapse) will be presented by treatment group.
- Analysis of TFR (protocol-defined relapse) will be performed using the stratified log-rank test.

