5.14 Determination of Sample Size

Approximately 70 subjects need to be recruited and randomized in a 1:1 ratio to the two treatment groups (SA237 and placebo). The sample size considerations are based on the following assumptions:

- A two-sided log-rank test
- 80% power at the 5% significance level
- A 66.5% reduction in the risk of relapse, i.e. the TFR hazard ratio of SA237 over placebo is 0.335
- TFR in the placebo arm following an exponential distribution, with hazard rate for one year $h(t) = 0.4184$
- A 2-year dropout rate of 10%

Based on the assumptions, 26 TFR events are needed for the primary analysis. TFR events are defined as protocol-defined relapses confirmed by the CEC with EDSS/FSS assessment performed by the examining assessor within 7 days after relapse symptoms were reported to site by the subject. The maximum accrual rate is estimated to be approximately 8 subjects per month, after the FPI plus 8 months of ramp up. The 70 subjects enrolled over one year and followed for an additional one and a half year will provide 26 TFR events. The primary analysis will be performed once 26 TFR events have been observed. Sponsor will conduct blind review during the double-blind period and might take appropriate action based on blind review.

Since the annualized relapse rate (ARR) is the number of relapse counts observed when every subject is observed for a year and suppose that the distribution follows a Gamma-Poisson distribution and that the mean and variance ratio (variance / mean) is a constant value of $\sqrt{2}$. The ratio was estimated using MS trials' data^{1,2)} because there are no approved medications for NMO.

Because the mean ARR of NMO subjects is estimated at 0.753³⁾ and eligibility criterion 2 says more than one ARR subjects are selected, we calculate the zero-truncated mean of the Gamma-Poisson distribution with the mean of 0.75 and the mean and variance ratio of $\sqrt{2}$, then the baseline ARR is estimated at 1.6. The two phase III MS trials above reported that pre- and post- baseline ARR in the placebo group were 1.4 and 0.4, so the post-baseline ARR in placebo group in this trial is estimated at 0.5.

Using the proportion of zero under supposed ARR distribution, we estimate the relapse-free rate at a year in placebo group at 65.8%. The relapse-free rate is assumed to follow the exponential distribution with a constant hazard, and then we set the hazard for one year of 0.4184 in placebo group.

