7.4 Step to identify the Day of baseline treatment increase/change:

[Step]

1. Identify “Relapse prevention therapy used at BL (i.e. Drug A)”.
2. Identify “Relapse prevention therapy* newly used from BL by the potential censored Day** other than the Day of increase/change of BL treatment (i.e. Drug B)”.
 - ✓ End if there is no Drug B.
3. Scientifically/medically evaluate if any of following information of Drug A are different from those of Drug B:
 - i. Dose regimen
 - ii. Drug name
 - ✓ End if not different.
 - ✓ If different, the earliest start Day of Drug B is the Day of dose increase/change of baseline treatment.

*; Including immunosuppressants and corticosteroids which were not used for relapse prevention (i.e. the indication is AE or Medical History etc). For them, route and duration of administration etc. will also be considered in step No.3 (e.g. temporal local administration will not be considered as increase/change of Drug A).

**; Including following days;

- a. 1st Day of rescue therapy started in the double-blind period for this patient (if any)
- b. The relapse onset Day of the event*** for this patient (if any)
- c. Clinical cut-off Day (CCOD): the relapse onset day of the event*** with the 26th earliest onset date
- d. Day of discontinuation from the double-blind period for this patient (e.g. Day of WD visit, Day of consent withdrawal) (if any)

***; the relapse adjudicated as protocol-defined relapse by Clinical Endpoint Committee (CEC) and EDSS/FSS assessed within 7 days from the date when the patient first reported symptoms to the site.

[Note]

- Day 1 = Baseline in the double blind period
- There may be more than one Drug B.
- Drug A must meet both of followings:
 - ✓ “Day of medication started” ≤ 1
 - ✓ “Day of medication stop” ≥ 1
- Drug B must meet both of followings:
 - ✓ “Day of medication started” ≥ 1
 - ✓ “Day of medication started” $<$ “potential censored Day***”

7.5 Procedure to identify the clinical relapse of optic neuritis occurred in the double-blind period:

The clinical relapse of optic neuritis occurred in the double-blind period of SA-307JG study will be identified by satisfying with either or both of followings. The Relapse Assessment Form (RAF) completed by study sites will be used for the identification.

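### First-of-month imputation of medication start dates is not kept out of TFR censoring, so a confirmed relapse can end up censored before its own onset

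*SAP*

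**What the plan says.** **Imputation.** SAP 5.3 states: "For the partial missing situation (month or day missing), the value will be imputed for the analysis purpose". A missing start day becomes the 1st and a missing month becomes January; a date without a year stays missing. On scope it says "These rules apply to AE and concomitant medication". The consistency check that follows is stated for AEs only and does not name relapse onset. The one efficacy exemption covers visit data.

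**Source of the dates.** Protocol 4.4 collects relapse-prevention and rescue therapy, with first administration date, in the Concomitant Medications part of the eCRF.

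**Censoring.** SAP 5.10.2 censors TFR at the earliest of three dates: the end of the double-blind period, a switch or increase of baseline treatment, or "receiving rescue therapy for clinical relapse". It makes no exception for rescue of a relapse that itself qualifies as an event. Protocol 6.5.1 and 6.9 are narrower: they censor at rescue only when there is no qualifying protocol-defined relapse. For a switch or increase of baseline treatment, the protocol has no such limit.

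**Baseline-treatment date.** SAP Appendix 7.4 looks for a newly used drug (Drug B) starting on or after Day 1 and before the potential censoring day, a list that includes relapse onset. If Drug B differs from the baseline drug, "the earliest start Day of Drug B is the Day of dose increase/change of baseline treatment". The same appendix sets the clinical cut-off at the 26th qualifying onset.

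**The concern.** Rescue, and any step-up of baseline treatment prompted by a relapse, comes after that relapse begins. Moving an incomplete start date back to the 1st can reverse the order. The patient is then censored before the relapse that led to the treatment, so censoring is caused by the outcome itself.

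The baseline-treatment route shows this most clearly. A corticosteroid started after the relapse is excluded from Drug B on its true date, because it starts after onset. Dated to the 1st, it can fall before onset, qualify as Drug B, and set the censoring day. Such treatment is foreseeable, since Protocol 4.4.1 permits more intensive oral corticosteroid treatment after a double-blind relapse than before one.

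At stake is the count of primary events in a trial powered on 26.

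**Working it through.** **1. The plan's own figure.** Inputs from SAP 5.14: "A two-sided log-rank test", "80% power at the 5% significance level", hazard ratio 0.335, 1:1 allocation. Schoenfeld's formula gives

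d = 4 × (1.960 + 0.842)² / (ln 0.335)² = 4 × 7.85 / 1.196 = 26.25,

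which agrees with the stated 26 (27 if rounded up).

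**2. How a date is reversed.** Relapse onset is 12 May and rescue is recorded as May only. The imputed date is 1 May, 11 days before onset. The earliest-date rule then censors at 1 May.

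**3. How often, given a missing day.** The imputed date falls before onset when treatment starts in the same calendar month as onset and onset is not on the 1st. With onset uniform over the month and an onset-to-treatment lag of L days, the share is about 1 − (L + 1)/30.4. Enumerating every onset day over four years gives:

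| Assumed lag (days) | Before onset | Same day | After onset |
|---|---|---|---|
| 0 | 96.7% | 3.3% | 0% |
| 3 | 86.9% | 3.3% | 9.9% |
| 7 | 73.7% | 3.3% | 23.0% |
| 14 | 50.7% | 3.3% | 46.0% |

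With month and day both missing (1 January), 98% to 99.7% fall before onset for lags of 0 to 7 days. Some of these would also fall before Day 1, and Appendix 7.4 would then not count them as Drug B.

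**4. Power per lost event.** Power = Φ(√d/2 × |ln 0.335| − 1.96), with |ln 0.335| = 1.0936:

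- d = 26: Φ(2.788 − 1.96) = 79.6%
- d = 25: Φ(2.734 − 1.96) = 78.1%
- d = 24: Φ(2.679 − 1.96) = 76.4%
- d = 23: 74.6%; d = 22: 72.7%

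**5. Range over the unknown frequency.** The documents give no rate of partial dates. Assume all 26 events are treated, a share f lacks the day, and 74% to 97% of those are reversed (lags of 7 to 0 days). Expected loss is 26 × f × that share:

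| f | Events lost | Power |
|---|---|---|
| 0% | 0 | 79.6% |
| 2% | 0.4–0.5 | about 79% |
| 5% | 1.0–1.3 | about 78% |
| 10% | 1.9–2.5 | 75–77% |
| 20% | 3.9–5.0 | 71–73% |

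**6. Which arm.** Use the planned hazards (0.4184 and 0.335 × 0.4184 = 0.1402 per year), 35 patients per arm, one year of uniform accrual plus 1.5 years, and 10% dropout over two years. Expected events are 18.9 placebo and 8.1 active, 27.0 in all, so 70% are placebo, or about 18 of 26. Losing one placebo event multiplies the crude rate ratio by 18/17 = 1.06 (0.335 becomes 0.355). Losing one of 8 active events multiplies it by 7/8.

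**The case against.** The link to TFR is inferred. No section says that dates imputed under SAP 5.3 are used to derive TFR censoring. SAP 5.10.1.3 sends the reader to 5.10.2 for the primary endpoint, and neither 5.10.2 nor Appendix 7.4 refers back to 5.3. That section opens with prior versus concomitant classification, where first-of-month is routine. This stands as a statement of what is unwritten. It does not close the gap, because the imputation is declared for analysis in general, covers these records, and exempts only visit data.

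The protocol's rescue rule keeps the event. That is right for rescue if the protocol governs, but SAP 5.10.2 is worded more broadly. It gives no protection on the baseline-treatment route.

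Partial dates should be rare. Protocol 4.4 makes the first administration date mandatory, Protocol 7.1 and 7.3 provide for data queries and source verification, and each potential relapse goes to the CEC. Protocol 4.5.3.2 allows that "the patient can visit a local clinic/hospital for immediate management of a relapse", but also tells the site to make every effort to obtain those records. This stands: the number may be zero. A mandatory field is not, however, stated to require a complete date, and SAP 5.3 provides for partial ones.

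A sensitivity analysis would recover the event. TFR to treated clinical relapse counts rescued relapses as events, so an event lost through rescue would reappear there. One lost through baseline-treatment change would not, since the other censoring rules carry over. The evaluation step in Appendix 7.4 looks mainly at regimen and drug name, not at whether the date was imputed.

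A reader might infer that every rescue with an unknown day is dated before its relapse and that the event is always lost. The documents do not support that. The order survives when treatment starts in a later month or onset is on the 1st, and the loss depends on imputed dates being used and the earliest-date rule being applied literally.

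**Conclusion.** The point holds as a gap in the rules: read literally, they permit a CEC-confirmed relapse to be censored before its onset, and nothing written prevents it. The rescue route is conditional on SAP 5.10.2 prevailing over Protocol 6.5.1 and 6.9; the baseline-treatment route is not. A lost event is not replaced, because the cut-off counts qualifying onsets whatever the censoring derivation does with them.

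The size is modest: about 1.5 to 2 power points per event, with the number of events unknown and possibly zero. Most lost events would be placebo events, and each of those pulls the estimate toward no effect, so this is not a false-positive concern. If the loss were strictly proportional in the two arms, the rate ratio would barely move and the cost would be mainly power. Lags and partial-date rates above are assumptions.

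A reader might also infer that the same rule wrongly shifts AEs from SA237 to placebo. I do not carry that forward: SAP 5.3 does reconcile AE dates with the first treatment date, and assigning ambiguous AEs to SA237 would be a conservative convention, not a correction.

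**What to change.** 1. State in SAP 5.3 and 5.10.2 that first-of-month imputation is not used for TFR censoring dates. Add that an incomplete start date of rescue or changed relapse-prevention therapy recorded as given for a relapse is not set earlier than the onset of that relapse. The bound must be tied to the relapse the drug treated. Tying it to any relapse compatible with the month could turn rescue of an earlier, non-qualifying relapse, which is a proper censoring date, into an event.
2. Align SAP 5.10.2 with Protocol 6.5.1 so that a qualifying relapse takes precedence over its own rescue.
3. Query incomplete dates for these drugs and review what remains, blinded, before database lock.

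The cost is a few lines of SAP text and minor programming. The sample size does not change: with the fix the analysis keeps 26 events and 79.6% power.

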5.4 Study Subjects

5.4.1 Disposition of Subjects

Summary tables of subject disposition will be provided as follows:

- A summary table of the number of subjects who were randomized to study treatment, number of subjects receiving at least one dose of study drug, number of subjects ending the double-blind period, number of withdrawal from the double-blind period, reason for withdrawal in the double-blind period, number of subjects entering the safety follow-up after double-blind period, number of subjects finishing the safety follow-up after double-blind period, number of subjects entering the open-label extension period, number of withdrawal from the extension period, reason for withdrawal in the extension period, number of subjects conducting last observation visit or withdrawal visit will be provided by treatment group and overall for both the blinded period and the open label extension.
- A by-subject listing of disposition status, including the date of informed consent, date of treatment with study drug and study completing/withdrawal, and reason for withdrawal from treatment and from study.

5.4.2 Protocol Deviations

Major protocol deviations are defined as those deviations from the protocol that are likely to have an impact on the subject's rights, safety, well-being, and/or on the validity of the data for analysis. The impact of major protocol deviations on the efficacy results will be investigated by assessing the robustness of the study results and conclusions to the choice of analysis population (see Section 5.5), both including and excluding data potentially affected by major protocol deviations.

A summary table and listing of protocol deviations will be provided as follows:

- The number and percentage of subjects without any deviation, without any major deviation, with at least 1 major deviation, type of major deviations will be summarized by randomized treatment group, overall and by site.
- A by-subject listing of protocol deviations will be presented.

5.5 Analysis Populations

The intent-to-treat (ITT) population will serve as the primary population for the analysis of efficacy, which consists of all randomized subjects. Subjects will be analyzed as randomized for analysis purposes. In case even a subject is incorrectly stratified at time of randomization, the analysis will be performed using the stratification for randomization.

The Per-Protocol Set population (PPS) will include all subjects in the ITT population who received at least 3 doses of study drug, and without any major protocol deviations which are considered to have an impact on efficacy. Subjects will be analyzed as treated for analysis purposes in the PPS.

The Safety Set (SAF) population will include all randomized subjects who have received at least one dose of active study drug or placebo. Subject will be included in the treatment group corresponding to the trial treatment they actually received for the analysis of safety data using the SAF population, i.e. patients who received at least one dose of SA237 will be assigned to the SA237 treatment arm, irrespective of randomized arm. .

The All-Subjects-Treated (All SA237) population will be defined as all enrolled subjects who took at least one dose of active study drug at any time. Date of the first active study drug administration will be defined as Day 1 for All SA237 analysis (i.e. Day 1 of subjects allocated in placebo group is redefined on the day of first dose of SA237 when entering extension period.

The Pharmacokinetics Per-Protocol Set (PK-PPS) and immunogenicity (anti-SA237 antibody; ADA) will include all subjects in the SAF with at least 1 valid post-dose concentration result with a dosing record and sampling time. Pharmacodynamics variables will be analyzed using the SAF population.

The Adolescents population will be defined as all enrolled subjects from 12 to 17 years old (< 18 years) at the first informed consent. After the total number of protocol-defined relapses judged by the CEC reaches 26, the recruitment period for the adolescents may be continued in the extension period until a minimum of 8 adolescents are enrolled into the study.

The following summary and listing will be provided:

- A summary of analysis populations, including the number and percentage of subjects in the defined analysis sets by treatment group and overall.
- A by-subject listing of analysis population (ITT, PPS, SAF, All SA237, PK-PPS, Adolescents Population, and PK-Adolescents Population) information will be provided.

This listing should include: subject number, inclusion/exclusion flag for each population and reason for exclusion from each population.

Subgroup analysis will be conducted based on the following variables:

- Age category (<18, ≥18 years)
- NMO/NMOSD and AQP4 Status at screening (5 categories: NMO, NMOSD, NMO and AQP4 positive, NMO and AQP4 negative, and NMO/NMOSD and AQP4 positive)
- Baseline treatment (azathioprine, mycophenolate mofetil, oral corticosteroids, azathioprine + oral corticosteroids, mycophenolate mofetil + oral corticosteroids)
- Baseline ARR (1, >1) based on the last two years before screening
- Geographic region (Asia, Europe/other)
- Japanese, Non-Japanese subjects
- ADA status (ADA negative subjects, ADA unaffected subjects, Treatment-boosted ADA subjects, Treatment-induced ADA subjects) (see Section 5.13)

For safety analyses, baseline weight (<median, ≥median) will be included in addition.

